#### D. STUDY POPULATION

The participating Data Partners in this protocol are Aetna and HealthCore. The dates of data availability differ by Data Partner (Table 1). The study population will consist of females ages 18 through 34 years who received TIV in the 4 weeks prior to or during pregnancy, and whose pregnancies have ended in an SAB (cases) or live delivery (controls). Women whose pregnancies have ended in a therapeutic abortion, ectopic or molar pregnancy, or stillbirth will not be used as controls since we will not be able to accurately assess gestational age using claims-based data. The study population will be further restricted to women with continuous enrollment from 90 days prior to pregnancy start through the SAB date in cases or index date in controls. Though we do not anticipate this to occur frequently, cases and controls who receive an additional influenza vaccine in the 90 days prior to the start of the study period of interest (i.e., -4 weeks gestation) will be excluded.

Data Partner	Date Data Available in Mini- Sentinel Common Data Model	Requirements for Data Used in Protocol 
Data Partner A	1/1/2008 through 10/31/2012	Vaccinations occurring in 2008-09 and 2010-11 influenza seasons
Data Partner B	1/1/2004 through 11/30/2011	Vaccinations occurring in 2008-09 and 2010-11 influenza seasons

Table 1: Dates of Data Availability by Data Partner

Influenza season defined as September 1 through April 30 of the following year. 2009-10 influenza season not included due to the availability of H1N1 influenza vaccine in the same season.

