654.11	ICD9	TUMORS OF BODY OF UTERUS, DELIVERED
654.12	ICD9	TUMORS BODY UTERUS DELIVERED W/MENTION PPC
654.21	ICD9	PREV C/S DELIV DELIV W/WO MENTION ANTPRTM COND
654.31	ICD9	RETROVERTED&INCARCERATED GRAVID UTERUS DELIVERED
654.32	ICD9	RETROVRT&INCARCERAT GRAVD UTRUS DELIV W/ PPC
654.41	ICD9	OTH ABN SHAPE/PSTN GRAVD UTRUS&NGHBR STRCT DELIV
654.42	ICD9	OTH ABN SHAPE/POS GRAVID UTERUS DEL W/PP COMPL
654.51	ICD9	CERVICAL INCOMPETENCE, DELIVERED
654.52	ICD9	CERVICAL INCOMPETENCE DELIVERED W/MENTION PPC
654.61	ICD9	OTH CONGENITAL/ACQUIRED ABNORM CERVIX W/DELIVERY
654.62	ICD9	OTH CONGEN/ACQ ABNORM CERV DELIV W/MENTION PPC
654.71	ICD9	CONGENITAL/ACQUIRED ABNORM VAGINA W/DELIVERY
654.72	ICD9	CONGEN/ACQ ABNORM VAGINA DELIVERED W/MENTION PPC
654.81	ICD9	CONGENITAL/ACQUIRED ABNORMALITY VULVA W/DELIVERY
654.82	ICD9	CONGEN/ACQ ABNORM VULVA DELIVERED W/MENTION PPC
654.91	ICD9	OTH&UNSPEC ABNORM ORGN&SOFT TISSUES PELV W/DELIV
654.92	ICD9	OTH&UNS ABN ORGN&SOFT TISS PELVIS DEL W/PP COMPL
655.01	ICD9	CNTRL NERV SYS MALFORMATION IN FETUS W/DELIVERY
655.11	ICD9	CHROMOSM ABNORM FETUS AFFECT MGMT MOTH W/DELIV
655.21	ICD9	HEREDITARY DZ POSS AFFECT FETUS MGMT MOM W/DEL
655.31	ICD9	SPCT DAMGE FETUS VIRL DZ MOM AFFCT MGMT MOM DEL

Code	Туре	Description
655.41	ICD9	SPCT DAMGE FETUS OTH DZ MOM AFFCT MGMT MOM DEL
655.51	ICD9	SPCT DAMGE FETUS FROM RX AFFECT MGMT MOTH DELIV
655.61	ICD9	SPCT DAMGE FETUS FROM RAD AFFECT MGMT MOTH DELIV
655.71	ICD9	DECR FETAL MOVEMENTS AFFECT MGMT MOTH DELIV
655.81	ICD9	OTH KNOWN/SPCT FETAL ABNORM NEC MGMT MOTH DELIV
655.91	ICD9	UNSPEC FETAL ABNORM AFFECT MANAGEMENT MOTH DELIV
656.01	ICD9	FETAL-MATERNAL HEMORRHAGE WITH DELIVERY
656.11	ICD9	RHESUS ISOIMMUNIZATION AFFECT MGMT MOTH DELIV
656.21	ICD9	ISOIMMU OTH&UNS BLD-GRP INCOMPAT MGMT MOTH DELIV
656.31	ICD9	FETAL DISTRESS AFFECT MANAGEMENT MOTH DELIVERED
656.41	ICD9	INTRAUTERINE DEATH AFFECT MANAGEMENT MOTH DELIV
656.51	ICD9	POOR FETAL GROWTH AFFECT MANAGEMENT MOTH DELIV
656.61	ICD9	EXCESS FETAL GROWTH AFFECT MANAGEMENT MOTH DELIV
656.71	ICD9	OTH PLACENTAL CONDS AFFECT MANAGEMENT MOTH DELIV
656.81	ICD9	OTH SPEC FETAL&PLACNTL PROBS MGMT MOTH DELIV
656.91	ICD9	UNSPEC FETAL&PLACNTL PROB AFFECT MGMT MOTH DELIV
657.01	ICD9	POLYHYDRAMNIOS, WITH DELIVERY
658.01	ICD9	OLIGOHYDRAMNIOS, DELIVERED
658.11	ICD9	PREMATURE RUPTURE MEMBRANES PREGNANCY DELIVERED
658.21	ICD9	DELAY DELIV AFTER SPONT/UNSPEC RUP MEMB DELIV
658.31	ICD9	DELAY DELIV AFTER ARTFICL RUPTURE MEMB DELIV
658.41	ICD9	INFECTION OF AMNIOTIC CAVITY DELIVERED

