763.6	ICD9	FETUS OR NEWBORN AFFECTED PRECIPITATE DELIVERY
768.0	ICD9	FETAL DEATH D/T ASPHYX/ANOXIA BFOR LABR/UNS TIME
768.1	ICD9	FETAL DEATH FROM ASPHYXIA OR ANOXIA DURING LABOR
V27	ICD9	OUTCOME OF DELIVERY
V27.0	ICD9	OUTCOME OF DELIVERY SINGLE LIVEBORN
V27.1	ICD9	OUTCOME OF DELIVERY SINGLE STILLBORN
V27.2	ICD9	OUTCOME OF DELIVERY TWINS BOTH LIVEBORN

Code	Туре	Description			
V27.3	ICD9	OUTCOME DELIVERY TWINS 1 LIVEBORN& 1 STILLBORN			
V27.4	ICD9	OUTCOME OF DELIVERY TWINS BOTH STILLBORN			
V27.5	ICD9	OUTCOME DELIVERY OTH MULTIPLE BIRTH ALL LIVEBORN			
V27.6	ICD9	OUTCOME DELIV OTH MULTIPLE BIRTH SOME LIVEBORN			
V27.7	ICD9	OUTCOME DELIV OTH MULTIPLE BIRTH ALL STILLBORN			
V27.9	ICD9	OUTCOME OF DELIVERY, UNSPECIFIED			
V30	ICD9	SINGLE LIVEBORN			
V30.0	ICD9	SINGLE LIVEBORN, BORN IN HOSPITAL			
V30.00	ICD9	SINGLE LIVEBORN HOSPITAL W/O C-SECTION			
V30.01	ICD9	SINGLE LIVEBORN HOSPITAL DELIV BY C-SECTION			
V30.1	ICD9	SINGLE LIVEBORN BORN BEFORE ADMISSION HOSPITAL			
V30.2	ICD9	SINGLE LIVEBORN BORN OUTSIDE HOSPITAL&NOT HOSP			
V31	ICD9	LIVEBORN TWIN BIRTH MATE LIVEBORN			
V31.0	ICD9	LIVEBORN TWIN-MATE LIVEBORN IN HOSPITAL			
V31.00	ICD9	LIVEBORN TWIN-MATE LIVEBORN HOSP W/O C-SEC			
V31.01	ICD9	LIVEBORN TWIN-MATE LIVEBORN HOSP C-SEC			
V31.1	ICD9	LIVEBORN TWIN-MATE LIVEBORN BEFORE ADMISS			
V31.2	ICD9	LIVEBORN TWIN-MATE LIVEBORN OUTSIDE HOSP			
V32	ICD9	LIVEBORN TWIN- MATE STILLBORN			
V32.0	ICD9	LIVEBORN TWIN-MATE STILLBORN HOSPITAL			
V32.00	ICD9	LIVEBORN TWIN-MATE STILLBORN HOSP W/O C-SEC			
V32.01	ICD9	LIVEBORN TWIN-MATE STILLBORN HOSPITAL C-SEC			
V32.1	ICD9	LIVEBORN TWIN-MATE STILLBORN BEFORE ADMISS			
V32.2	ICD9	LIVEBORN TWIN-MATE STILLB OUTSIDE HOSP&NOT HOSP			
V33	ICD9	LIVEBORN TWIN UNS WHETHER MATE LIVEBORN/STILLB			

Code	Туре	Description
V33.0	ICD9	LIVEBORN TWIN-UNS MATE LIVEBORN/STILLB HOSP
V33.00	ICD9	LIVEB TWIN-UNS MATE LIVEB/STILLB-HOSP W/O C-SEC
V33.01	ICD9	TWIN UNS MATE STILLB/LIVEB BORN HOS DEL C/S DEL
V33.1	ICD9	LIVB TWIN-UNS MATE LIVEB/STILLB-BEFORE ADMISS
V33.2	ICD9	LIVEB TWIN-UNS MATE LIVEB/STILLB OUTSIDE HOSP
V34	ICD9	LIVEBORN OTH MULTIPLE MATES ALL LIVEBORN
V34.0	ICD9	LIVEBORN OTH MULTIPLE-MATES LIVEBORN HOSPITAL
V34.00	ICD9	OTH MX MATES ALL LIVEB BORN HOS DEL W/O C/S DEL
V34.01	ICD9	LIVEBORN OTH MX-MATES LIVEBORN HOSP C-SEC
V34.1	ICD9	LIVEBORN OTH MX-MATES LIVEBORN BEFOR ADMISSION
V34.2	ICD9	LIVEBORN OTH MX-MATES LIVEBORN OUTSIDE HOSP
V35	ICD9	LIVEBORN OTHER MULTIPLE MATES ALL STILLBORN

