Sexually transmitted infection	098.85	OTHER GONOCOCCAL HEART DISEASE
Sexually transmitted infection	098.86	GONOCOCCAL PERITONITIS
Sexually transmitted infection	098.89	GONOCOCCAL INFECTION OF OTHER SPECIFIED SITES
Sexually transmitted infection	099.0	CHANCROID
Sexually transmitted infection	099.1	LYMPHOGRANULOMA VENEREUM
Sexually transmitted infection	099.2	GRANULOMA INGUINALE
Sexually transmitted infection	099.3	REITERS DISEASE
Sexually transmitted infection	099.4	OTHER NONGONOCOCCAL URETHRITIS
Sexually transmitted infection	099.40	UNSPECIFIED NONGONOCOCCAL URETHRITIS
Sexually transmitted infection	099.41	NONGONOCOCCAL URETHRITIS DUE
Sexually transmitted infection	099.49	CHLAMYDTRACHOMATIS NONGONOCOCCAL URETHRITIS DUE OTHER SPEC ORGANISM
, Sexually transmitted infection	099.50	CHLAMYDIA TRACHOMATIS INFECTION UNSPECIFIED SITE
Sexually transmitted infection	099.51	CHLAMYDIA TRACHOMATIS INFECTION OF PHARYNX
, Sexually transmitted infection	099.52	CHLAMYDIA TRACHOMATIS INFECTION OF ANUS&RECTUM
Sexually transmitted infection	099.53	CHLAMYDTRACHOMATIS INFECTION LOWER GU SITES
Sexually transmitted infection	099.54	CHLAMYDTRACHOMATIS INFECTION OTH GU SITES
Sexually transmitted infection	099.55	CHLAMYDTRACHOMATIS INFECTION UNSPEC GU SITE
Sexually transmitted infection	099.56	CHLAMYDIA TRACHOMATIS INFECTION OF PERITONEUM
' Sexually transmitted infection	099.59	CHLAMYDIA TRACHOMATIS INFECTION OTHER SPEC SITE
, Sexually transmitted infection	099.8	OTHER SPECIFIED VENEREAL DISEASES
Sexually transmitted infection	099.9	UNSPECIFIED VENEREAL DISEASE
Sexually transmitted infection	647.00	MATERNAL SYPHILIS-COMPLICATING PC/P-UNS EOC
Sexually transmitted infection	647.01	MATERNAL SYPHILIS COMP PREGNANCY W/DELIVERY
Sexually transmitted infection	647.02	MTRN SYPHILIS COMP PG W/DELIV W/CURRENT PPC
Sexually transmitted infection	647.03	MATERNAL SYPHILIS. ANTEPARTUM
Sexually transmitted infection	647.04	MATERNAL SYPHILIS POSTPARTUM CONDITION/COMPLICAT

Confounder	Code	Description	
Sexually transmitted infection	647.1	MTRN GONORRHEA COMP PG CHILDBIRTH/THE PUERPERIUM	
Sexually transmitted infection	647.10	MATERNAL GONORRHEA-COMPLICATING PC/P-UNS EOC	

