Sexually transmitted infection	647.11	DescriptionMTRN GONORRHEA COMP PG CHILDBIRTH/THE PUERPERIUMMATERNAL GONORRHEA-COMPLICATING PC/P-UNS EOCMATERNAL GONORRHEA WITH DELIVERYMATERNAL GONORRHEA W/DELIVERY W/CURRENT PPCMATERNAL GONORRHEA, ANTEPARTUMMATERNAL GONORRHEA, ANTEPART CONDITION/COMPLICATOTH MATERNAL VENEREAL DZ-COMPLICAT PC/P-UNS EOCOTHER MATERNAL VENEREAL DISEASES WITH DELIVERYOTH MATERNAL VENEREAL DZ W/DELIV W/CURRENT PPCOTH MATERNAL VENEREAL DZ W/DELIV W/CURRENT PPCOTH MATERNAL VENEREAL DZ W/DELIV W/CURRENT PPCOTH MATERNAL VENEREAL DISEASE ANTPRTM COND/COMPLOTHER VENEREAL DISEASES POSTPARTUM COND/COMPLCHRONIC PYELONEPHRITISCHRON PYELONEPHRITIS W/O LES RENL MEDULRY NECROSACUT PYELONEPHRITIS W/O LES RENAL MEDULRY NECROSACUT PYELONEPHRITIS W/O LES RENAL MEDULRY NECROSACUT PYELONEPHRITIS W/LES RENAL MEDULRY NECROSRENAL AND PERINEPHRIC ABSCESSPYELOURETERITIS CYSTICA	
Sexually transmitted infection	647.12	MATERNAL GONORRHEA W/DELIVERY W/CURRENT PPC	
Sexually transmitted infection	647.13	MATERNAL GONORRHEA, ANTEPARTUM	
Sexually transmitted infection	647.14	MATERNAL GONORRHEA POSTPART CONDITION/COMPLICAT	
Sexually transmitted infection	647.20	OTH MATERNAL VENEREAL DZ-COMPLICAT PC/P-UNS EOC	
Sexually transmitted infection	647.21	OTHER MATERNAL VENEREAL DISEASES WITH DELIVERY	
Sexually transmitted infection	647.22	OTH MATERNAL VENEREAL DZ W/DELIV W/CURRENT PPC	
Sexually transmitted infection	647.23	OTH MATERNAL VENEREAL DISEASE ANTPRTM COND/COMPL OTHER VENEREAL DISEASES POSTPARTUM COND/COMPL	
Sexually transmitted infection	647.24	OTHER VENEREAL DISEASES POSTPARTUM COND/COMPL	
Urinary tract infection	590.0	CHRONIC PYELONEPHRITIS	
Urinary tract infection	590.00	CHRON PYELONEPHRITIS W/O LES RENL MEDULRY NECROS	
Urinary tract infection	590.01	CHRON PYELONEPHRITIS W/LES RENAL MEDULRY NECROS	
Urinary tract infection	590.1	ACUTE PYELONEPHRITIS	
Urinary tract infection	590.10	ACUT PYELONEPHRITIS W/O LES RENAL MEDULRY NECROS	
Urinary tract infection	590.11	ACUT PYELONEPHRITIS W/LES RENAL MEDULRY NECROS	
Urinary tract infection	590.2	RENAL AND PERINEPHRIC ABSCESS	
Urinary tract infection	590.3	PYELOURETERITIS CYSTICA	
Urinary tract infection	590.80	UNSPECIFIED PYELONEPHRITIS	
Urinary tract infection	590.81	PYELITIS/PYELONEPHRITIS DISEASES CLASSIFIED ELSW	
Urinary tract infection	590.9	UNSPECIFIED INFECTION OF KIDNEY	
Urinary tract infection	59000	AMNIOCENTESIS DIAGNOSIC	
Urinary tract infection	59001	AMNIOCENTESISS THER AMNIOTIC FLUID RDCTJ US GID	

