Urinary tract infection	595.0	ACUTE CYSTITIS	
Urinary tract infection	595.1	CHRONIC INTERSTITIAL CYSTITIS	
Urinary tract infection	595.2	OTHER CHRONIC CYSTITIS	
Urinary tract infection	595.4	CYSTITIS IN DISEASES CLASSIFIED ELSEWHERE	

Confounder	Code	Description
Urinary tract infection	595.89	OTHER SPECIFIED TYPES OF CYSTITIS
Urinary tract infection	595.9	UNSPECIFIED CYSTITIS
Urinary tract infection	597.0	URETHRAL ABSCESS
Urinary tract infection	597.80	UNSPECIFIED URETHRITIS
Urinary tract infection	597.89	OTHER URETHRITIS
Urinary tract infection	599.0	URINARY TRACT INFECTION SITE NOT SPECIFIED
Urinary tract infection	646	OTHER COMPLICATIONS OF PREGNANCY NEC
Urinary tract infection	646.60	INFS GU TRACT PREGNANCY UNSPEC AS EPIS CARE
Urinary tract infection	646.61	INFECTIONS GENITOURINARY TRACT PREGNANCY W/DELIV
Urinary tract infection	646.62	INFS GU TRACT PREGNANCY W/DELIV W/CURRENT PPC
Urinary tract infection	646.63	INFECTIONS OF GENITOURINARY TRACT ANTEPARTUM
Urinary tract infection	646.64	INFECTIONS GU TRACT POSTPARTUM COND/COMPL
Urinary tract infection	647.0	MTRN SYPHILIS COMP PG CHILDBIRTH/THE PUERPERIUM

Appendix 6: CPT, CVX, and HCPCS codes for identifying exposure to trivalent influenza vaccine prior to the 2013-14 season

Code	Туре	Description 
90655	СРТ	INFLUENZA VIRUS VACCINE, SPLIT VIRUS, PRESERVATIVE FREE, FOR CHILDREN 6-35
		MONTHS OF AGE, FOR INTRAMUSCULAR USE
90656	СРТ	INFLUENZA VIRUS VACCINE, SPLIT VIRUS, PRESERVATIVE FREE, FOR USE IN
		INDIVIDUALS 3 YEARS OF AGE AND ABOVE, FOR INTRAMUSCULAR USE
90657	CPT	INFLUENZA VIRUS VACCINE, SPLIT VIRUS, FOR CHILDREN 6-35 MONTHS OF AGE,
		FOR INTRAMUSCULAR USE
90658	CPT	INFLUENZA VIRUS VACCINE, SPLIT VIRUS, FOR USE IN INDIVIDUALS 3 YEARS OF AGE
		AND ABOVE, FOR INTRAMUSCULAR USE
90659	CPT	INFLUENZA VIRUS VACCINE, WHOLE VIRUS, FOR INTRAMUSCULAR OR JET
		INJECTION USE
90662	CPT	INFLUENZA VIRUS VACCINE, SPLIT VIRUS, PRESERVATIVE FREE, ENHANCED
		IMMUNOGENICITY VIA INCREASED ANTIGEN CONTENT, FOR INTRAMUSCULAR USE
15	CVX	INFLUENZA, SPLIT (INCL. PURIFIED SURFACE ANTIGEN)
16	CVX	INFLUENZA, WHOLE
135	CVX	INFLUENZA, HIGH DOSE SEASONAL
140	CVX	INFLUENZA, SEASONAL, INJECTABLE, PRESERVATIVE FREE
141	CVX	INFLUENZA, SEASONAL, INJECTABLE
Q2034	HCPCS	INFLUENZA VIRUS VACCINE, SPLIT VIRUS, FOR INTRAMUSCULAR USE (AGRIFLU)
Q2035	HCPCS	INFLUENZA VIRUS VACCINE, SPLIT VIRUS, WHEN ADMINISTERED TO INDIVIDUALS 3
		YEARS OF AGE AND OLDER, FOR INTRAMUSCULAR USE (AFLURIA)

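### Four rows in the urinary tract infection list of Appendix 5 are not urinary infections, and Appendix 3 counts stillbirth and fetal-death codes as live deliveries

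*Protocol*

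**What the plan says.** **Infections.** Section III.H says that cases and controls will, if controls suffice, be matched on several infections, UTI among them, in the 1-28 days before the SAB or index date. The infections are to be found in ICD-9-coded data through Appendix 5. In the UTI group of that appendix:
- 59000 is described as "AMNIOCENTESIS DIAGNOSIC";
- 59001 is described as "AMNIOCENTESISS THER AMNIOTIC FLUID RDCTJ US GID";
- 646 is described as "OTHER COMPLICATIONS OF PREGNANCY NEC";
- 647.0 is described as "MTRN SYPHILIS COMP PG CHILDBIRTH/THE PUERPERIUM".

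The five-digit syphilis codes 647.00 to 647.04 (the first reads "MATERNAL SYPHILIS-COMPLICATING PC/P-UNS EOC") are in the sexually transmitted infection group of the same appendix. Section IV.A, Primary Objective 3, reports the PPV of each confounder matched upon and the share of matched pairs that agree on it in the chart.

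**Deliveries.** Section III.F.2 uses Appendix 3 to identify live deliveries as potential controls. Appendix 3 includes V27.1, described as "OUTCOME OF DELIVERY SINGLE STILLBORN", together with V27.4 and V27.7 (twins or other multiples, all stillborn), 768.0 and 768.1 (fetal death), and 656.41, described as "INTRAUTERINE DEATH AFFECT MANAGEMENT MOTH DELIV". Section III.D lists the pregnancy endings that are ineligible as controls, ending with "or stillbirth will not be used as controls since we will not be able to accurately assess gestational age using claims-based data".

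**The concern.** The protocol's stated overall goal is to optimize algorithms for using claims and birth certificate data, and the code lists are part of those algorithms. A UTI flag set by a code for something else has two effects. It can pair women as alike on UTI when they are not, and it enters the PPV that Primary Objective 3 will report. A PPV shifted by a listing error would be read as a statement about the quality of claims data, and the list could be carried into later studies.

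The delivery list conflicts with the eligibility rule it is meant to serve. Section III.D excludes stillbirths because claims cannot date them reliably. Section III.H assigns 270 days of gestation when no gestational-age code from Appendix 4 is found. A stillbirth admitted through Appendix 3 could therefore be given a wrong pregnancy start and be proposed as a match on that date.

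**Working it through.** The plan states no figure on this point, so the check is a row count and a comparison of sections.

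**1. UTI rows in Appendix 5.**
- 590.x codes written with a decimal: 11
- 59000 and 59001: 2
- 595.x: 6
- 597.x: 3
- 599.0: 1
- 646: 1
- 646.60 to 646.64: 5
- 647.0: 1

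Total: 11 + 2 + 6 + 3 + 1 + 1 + 5 + 1 = 30. Rows whose description is not a urinary infection: 59000, 59001, 646 and 647.0, that is 4 of 30.

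**2. How each row could act.**
- *59000 and 59001.* The digits are those of 590.00 and 590.01 (chronic pyelonephritis), which are listed a few rows above. A lost decimal point is a plausible origin, but that is an inference. If only diagnosis fields are searched with decimals removed, the strings return 590.00 and 590.01 and do no harm. If code type is ignored, they also return amniocentesis procedures. Appendices 2, 3 and 6 have a column for code type and Appendix 5 has none, so the list does not settle which search is run.
- *646 and 647.0.* These have ICD-9 form, so restricting the search to diagnosis codes does not remove them. The protocol marks prefixes elsewhere with an asterisk (493* in III.H, 765.0* in Appendix 4), which suggests that unmarked codes are exact. On that reading, 646 and 647.0 act only when billed as such. If they were read as prefixes, 647.0 would place 647.00 to 647.04 in both infection groups, and 646 would take in unrelated codes such as 646.31 (recurrent pregnancy loss in Appendix 3).

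**3. Effect on the PPV.** Suppose n women are flagged by the other 26 rows, with t confirmed in the chart. Suppose m more are flagged only by the four rows, with u confirmed. Then

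PPV with the four rows = (t + u)/(n + m); PPV without them = t/n.

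The first is below the second exactly when u/m < t/n. A fall is the natural expectation, because the four rows do not describe a urinary infection. The protocol gives none of n, t, m or u, so no size can be attached.

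**4. Delivery rows in Appendix 3.** V27.1, V27.4 and V27.7 say outright that every infant was stillborn: 3 codes. 768.0, 768.1 and 656.41 describe fetal or intrauterine death: 3 codes. Total: 6. V27.3, V27.6 and the V32, V35 and V36 groups are left out of the count because at least one infant is liveborn.

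**5. What stops a stillbirth later.** Section V.B limits controls to mothers linked to a birth certificate or an infant plan record. Section III.I requires chart confirmation of live delivery before a control is kept. No step in Phase 1 (III.F) removes the six codes.

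**The case against.** The strongest defence has four parts.

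*UTI matching may never happen.* III.H makes it depend on having enough controls, III.K speaks of matching on further factors only if it is implemented, and the PPV is computed only for factors matched upon. This stands, although V.B states infection matching without the condition.

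*A search confined to ICD-9 data would not retrieve amniocentesis.* This also stands as the text of III.H is worded. It does not cover 646 or 647.0, and it leaves two rows that contradict the title of their own table.

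*A woman flagged by one of these rows may still have a UTI in her chart.* Correct. A reader might infer that every such woman is a false positive, so that the PPV is capped at some known value. The documents do not support that. Code 646 is the parent of 646.60 to 646.64, which are genuine genitourinary infection codes, and no counts are given from which a cap could be computed.

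*Stillbirths are screened out.* A reader might infer that stillbirths end up analysed as controls. The linkage requirement and the chart review in III.I should prevent that. Wasted control slots are also cushioned: up to six potential controls may be pursued per case (III.A, III.H), a case that loses both controls may be rematched, and when both qualify one is dropped at random (III.I).

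None of this explains or corrects the rows themselves.

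**Conclusion.** The lists are wrong as written, by the protocol's own descriptions. Four of 30 UTI rows are not urinary infections, with syphilis classified in two ways. Six Appendix 3 codes describe stillbirth or fetal death in a list meant for live deliveries, against III.D.

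For UTI, the consequence is possible misclassification in matching and a distorted PPV and pair concordance in Primary Objective 3. It assumes that infection matching is carried out and, for 59000 and 59001, that the search does not separate procedure codes from diagnosis codes. The size cannot be derived and may be small.

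For deliveries, the consequence is at most some wasted control selection and chart review, provided linkage and chart review work as described. It would go too far to say that all six codes mean no infant was liveborn: 656.41 does not say so, and Appendix 3 deliberately includes multiple pregnancies with a loss and a delivery (651.31, V27.3). The SAB case definition, the vaccine exposure definition and the SAB PPV of Primary Objective 1 are untouched.

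**What to change.** **Appendix 5:** delete 59000, 59001 and 646 from the UTI group, and move 647.0 to the sexually transmitted infections beside 647.00 to 647.04. Add a code-type column, as in Appendices 2, 3 and 6, so that only ICD-9 diagnosis codes are searched.

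**Appendix 3:** delete V27.1, V27.4, V27.7, 768.0, 768.1 and 656.41 as codes that qualify a record as a live delivery. Do not use 656.41 as an exclusion, because a multiple pregnancy carrying it may include a liveborn infant. Deletion alone does not catch a stillbirth that also carries a general delivery code such as 59409, so linkage and chart review must stay as they are.

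**Cost:** edits to ten rows (4 + 6) and one added column in two appendix tables, with the matching change in the extraction program.

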# Appendix 7: Considerations for choice of case-time-control design, as compared to the self-controlled case series approach

In developing this protocol, several key factors were considered in selecting the study design. At the forefront of the design choice were the case-time-control design and the self-controlled case series because of their inherent ability to control for confounding by time-constant or relatively time constant factors such as race/ethnicity and age (the latter since this is an adolescent/adult population). Several considerations were made in selecting the case-time-control design for the primary analysis, as outlined below.

#### 1. Time scale and addressing confounding by calendar time and gestational age

For this evaluation, exposure is defined on two time scales: time since vaccination and gestational age at vaccination. With a SCCS design, it is possible to examine the TIV-SAB association if defining the risk interval as time since vaccination and simultaneously adjusting for time-varying gestational age and calendar time in regression models. However, residual confounding by gestational age and calendar time might remain due to low case numbers in each stratum. Furthermore, because a woman's likelihood of vaccination could potentially decrease after a miscarriage, the key assumption of the SCCS of no change in probability of exposure across follow-up time is violated, such that additional methodological techniques would need to be used. With a SCCS, it is not possible to examine the TIV-SAB association if exposed person-time is defined by gestational age at vaccination.

In contrast, the case-time-control design allows one to examine the TIV-SAB association while defining exposed person-time by time since vaccination and by gestational age at vaccination in two iterations of the design. For both time scales, matching cases to controls on date of LMP adjusts for time trends in vaccination by calendar time and gestational age. Thus, the key reason that we chose the case-time-control design over the self-controlled case series is that it allows us to examine both exposure time scales (i.e., time since vaccination and gestational age at vaccination) while adjusting for seasonality and gestational age by matching, thereby avoiding residual confounding due to model misspecification.

